## 13 APPENDICES

### Appendix 1 Renal function

For assessment of renal function, serum creatinine is typically used after the first week of life in term neonates and after 4 weeks in pre-term neonates. Before then, intra-individual changes (related to post-menstrual age) in serum creatinine are used as a guide to renal function.

In addition, the following references should be considered:

- Schwartz and colleagues ([Schwartz 2009](#)) published the following modified formula (based on serum creatinine levels determined with the enzymatic method):  

$$\text{Estimated glomerular filtration rate (eGFR; mL/min/1.73 m}^2) = 0.413 \cdot \text{length (cm)} / \text{creatinine (mg/dL)}$$
- Abitbol and colleagues ([Abitbol 2014](#)) reported serum creatinine levels of  $0.68 \pm 0.14 \text{ mg/dL}$  during post-natal days 3–7 in 60 pre-term neonates ( $34 \pm 3$  weeks). The same report presented a graph of eGFRs calculated with the modified Schwartz formula, in which the values of all age groups were  $> 20 \text{ mL/min/1.73 m}^2$ . Of note, the creatinine-based equation underestimated the GFR compared to the CysC-based equations, especially in pre-term neonates.
- Two graphs presented at an EMA Workshop on regulatory and scientific issues related to the investigation of medicinal products intended for neonate use ([Van den Anker 2006](#)) indicated that serum creatinine levels in neonates with a body weight  $> 1000 \text{ g}$ , or a gestational age  $> 27$  weeks, fell from a maximum of about  $110 \text{ } \mu\text{mol/L}$  on day 1 to about  $50 \text{ } \mu\text{mol/L}$  within 3 to 4 weeks.

#### Conclusion

Serum creatinine levels are generally used to monitor renal function ([CHMP-PDCO 2009](#)). Glomerular filtration rate (GFR) is indirectly proportional to serum creatinine, i.e., a GFR of two-thirds of normal corresponds to a 1.5-fold greater than normal serum creatinine level. Since post-menstrual age is the best parameter of kidney maturation, the following creatinine thresholds (determined with the enzymatic method) may be used to support the evaluation of Exclusion criterion [7](#):

Post-menstrual age (weeks)	Creatinine (mg/dL)	Rationale
28 – 34 completed	1.32	150% of the upper limit of the laboratory normal ranges
35 – 42 completed	1.10	Arithmetic mean of 1.32 and 0.88
$> 42$	0.88	Upper limit of the laboratory normal ranges of the lower age groups and slightly more than 150% of $0.5 \text{ mg/dL}$ , the stable creatinine level during the first 2 years of life

Considering these serum creatinine thresholds, a GFR estimated with the modified Schwartz formula of less than the values given below might provide evidence of impaired renal function or known significant renal disease:

Length (cm)	eGFR threshold (mL/min/1.73 m  )		
	Post-menstrual age (weeks)		
	28 – 34 completed	35 – 42 completed	> 42
33	10.3	12.4	15.5
34	10.6	12.8	16.0
35	11.0	13.1	16.4
36	11.3	13.5	16.9
37	11.6	13.9	17.4
38	11.9	14.3	17.8
39	12.2	14.6	18.3
40	12.5	15.0	18.8
41	12.8	15.4	19.2
42	13.1	15.8	19.7
43	13.5	16.1	20.2
44	13.8	16.5	20.7
45	14.1	16.9	21.1
46	14.4	17.3	21.6
47	14.7	17.6	22.1
48	15.0	18.0	22.5
49	15.3	18.4	23.0
50	15.6	18.8	23.5
51	16.0	19.1	23.9
52	16.3	19.5	24.4
53	16.6	19.9	24.9
54	16.9	20.3	25.3
55	17.2	20.7	25.8
56	17.5	21.0	26.3
57	17.8	21.4	26.8
58	18.1	21.8	27.2
59	18.5	22.2	27.7
60	18.8	22.5	28.2

Investigators will exercise their clinical knowledge in conjunction with these thresholds when determining the applicability of Exclusion criterion 7 to potential participants in the study.

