#### 1.4.3 Dose rationale

A three-compartment pediatric population PK model with linear elimination, clearance dependent on glomerular filtration, and other PK parameters scaled to body weight using a fitted coefficient consistent with allometric scaling principles, provided a robust fit to pooled data from studies CSI-1006, BPR-PIP-001, and BPR-PIP-002. Pre-defined model qualification procedures indicated that the final population PK model was expected to provide reliable estimates of ceftobiprole plasma exposure in the pediatric patients enrolled in these studies, and that the model was appropriate for the conduct of model-based simulations designed to identify appropriate ceftobiprole dosing regimens in pediatric patients (Rubino 2021a).

Model-based simulation analyses conducted using the final population PK model suggest that the following dosing regimens are predicted to result in consistent ceftobiprole exposure and adequate PK-PD target attainment for pathogens with a ceftobiprole MIC of 4 µg/mL ( $\geq 97.1\%$  of the pediatric population with a %FT>MIC above 40%):

- ceftobiprole 10 mg/kg infused over 2 hours and administered q12h in neonates and infants aged  $< 3$  months with a body weight  $< 4$  kg
- ceftobiprole 15 mg/kg infused over 2 hours and administered q12h in neonates and infants aged  $< 3$  months with a body weight  $\geq 4$  kg
- ceftobiprole 15 mg/kg infused over 2 hours and administered q8h in infants and children aged  $\geq 3$  months to  $< 12$  years with a body weight  $< 33$  kg
- ceftobiprole 10 mg/kg infused over 2 hours and administered q8h in adolescents aged  $\geq 12$  to  $< 18$  years with a body weight  $< 50$  kg
- ceftobiprole 500 mg infused over 2 hours and administered q8h in children with a body weight  $\geq 33$  kg and adolescents with a body weight  $\geq 50$  kg

Model-based simulations also indicated that the dose should be adjusted based on body weight or maximum allowable dose to avoid overly high exposures in the lightest infants ( $< 4$  kg), children  $\geq 33$  kg, and adolescents  $\geq 50$  kg.

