#### **4.3 Exclusion criteria**

Patients who meet any of the following criteria must be excluded from the study:

1. History of a previous clinically relevant hypersensitivity or serious adverse reaction to beta-lactam antibiotics, or to aminoglycosides if intended to be used in combination with ceftobiprole
2. Viral, fungal, or parasitic pathogen as the sole reason for infection, OR known resistance of the causative bacterial pathogens to ceftobiprole
3. Refractory septic shock not responding to 60 minutes of vasopressor treatment within 48 hours before enrollment
4. Proven ventilator-associated pneumonia
5. Proven central nervous system infection (e.g., meningitis, brain abscess)
6. Proven osteomyelitis, infective endocarditis, or necrotising enterocolitis
7. Impaired renal function or known significant renal disease, as evidenced by an estimated glomerular filtration rate (using the Schwartz formula or other applicable formula) calculated to be less than 2/3 of normal for the applicable age group, OR urinary output  $< 0.5 \text{ mL/kg/h}$  (measured over at least 8 hours), OR requirement for dialysis
8. Significant laboratory abnormalities, including:
  - a) Hematocrit  $< 20\%$
  - b) Absolute neutrophil count  $< 0.5 \times 10^9/\text{L}$
  - c) Alanine aminotransferase (ALT) or aspartate aminotransferase (AST)  $> 8 \times$  the age-specific upper limit of normal
9. Progressively fatal underlying disease, or life expectancy  $< 30$  days
10. Documented history of convulsions

11. Severe immunodeficiency (congenital or acquired)
12. Use of systemic antibacterial therapy for longer than 72 hours within 7 days before start of study medication
13. Any condition including antepartum / peripartum factors or procedures, which would, in the opinion of the Investigator, make the patient or caregiver unsuitable for the study, putting the patient at risk or compromising the quality of the data
14. Participation in another clinical study with an investigational product within 30 days of enrollment in the current study

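### Appendix 1's creatinine limit above 42 weeks (0.88 mg/dL) is 176% of the stable level it cites, not just over 150%, so it is looser than the two-thirds GFR rule of Exclusion criterion 7 that it supports

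*Protocol*

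**What the plan says.** Protocol Section 4.3, criterion 7, excludes an infant whose estimated GFR is "calculated to be less than 2/3 of normal for the applicable age group". Low urine output and need for dialysis are separate limbs of the same criterion.

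The Conclusion of Appendix 1 turns the GFR limb into numbers. It first gives the conversion: "a GFR of two-thirds of normal corresponds to a 1.5-fold greater than normal serum creatinine level". It then tabulates creatinine limits by post-menstrual age:

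| Post-menstrual age (weeks) | Limit (mg/dL) | Reason given |
|---|---|---|
| 28–34 completed | 1.32 | 150% of the laboratory upper limit of normal |
| 35–42 completed | 1.10 | "Arithmetic mean of 1.32 and 0.88" |
| above 42 | 0.88 | "Upper limit of the laboratory normal ranges of the lower age groups and slightly more than 150% of" 0.5 mg/dL, described as "the stable creatinine level during the first 2 years of life" |

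A second table converts each limit into eGFR cut-offs for lengths of 33 to 60 cm, using the modified Schwartz formula. The limits are supportive: they "may be used to support the evaluation of Exclusion criterion" 7, and investigators are to apply clinical knowledge alongside them.

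**The concern.** The row above 42 weeks names its own normal level, 0.5 mg/dL. The appendix equates two-thirds of normal GFR with 1.5 times normal creatinine, which gives 0.75 mg/dL. The row prints 0.88. On the row's own numbers, an infant with creatinine above 0.75 and up to 0.88 mg/dL passes the supporting limit while failing the criterion it supports.

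This matters because exposure follows renal function. Section 1.4.3 describes "clearance dependent on glomerular filtration", and the simulations extended to pre-term neonates and young infants assumed normal renal function. Section 3.3.1 does not allow the dose to be modified, on the ground that moderate and severe renal impairment are screened out. Renal failure is an adverse event of special interest (Section 7.2.5), and safety is the primary endpoint in about eight infants.

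The appendix's caution about early creatinine does not cover this age band. It says that "serum creatinine is typically used after the first week of life in term neonates and after 4 weeks in pre-term neonates". A pre-term infant (born by 36+6) reaches 43+0 weeks no earlier than day 43, and a term infant born by 41+6 no earlier than day 8.

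**Working it through.** **Inputs (Protocol Appendix 1).** Limit above 42 weeks 0.88 mg/dL; stable level 0.5 mg/dL; GFR inversely proportional to creatinine; eGFR = 0.413 × length (cm) / creatinine (mg/dL).

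**1. The plan's figures that reproduce.**
- 1.5 × 0.88 = 1.32 mg/dL (28–34 weeks).
- (1.32 + 0.88)/2 = 1.10 mg/dL (35–42 weeks).
- All 84 eGFR cells (28 lengths × 3 columns) follow from the three limits to rounding, with a largest deviation of 0.05. At 45 cm, for example, 0.413 × 45/0.88 = 21.1. So 0.88 is what the authors used, and the cells are calculated correctly from it.

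**2. The figure that does not.** 0.88/0.5 = 1.76, or 176%. Fraction of normal GFR = 0.5/0.88 = 56.8%, against 66.7% required. The limit that matches the rule is 1.5 × 0.5 = 0.75 mg/dL.

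**3. Could rounding or another reference level explain it?** Micromoles are converted at an assumed 88.4 µmol/L per mg/dL, a factor the documents do not give.

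| Normal creatinine (mg/dL) | 0.88 as % of normal | GFR at 0.88, % of normal |
|---|---|---|
| 0.45 (lowest that rounds to 0.5) | 196% | 51% |
| 0.50 (as printed) | 176% | 57% |
| 0.55 (just above the highest that rounds to 0.5) | 160% | 62.5% |
| 0.57 (50 µmol/L, cited in Appendix 1 at 3–4 weeks) | 156% | 64% |
| 0.587 (= 0.88/1.5) | 150% | 67% |

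Rounding does not rescue the phrase. A normal of 0.57 would fit it, and about 0.59 would meet the rule, but the row states neither.

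**4. Effect on the eGFR column.** 0.88/0.75 = 1.173, so each cut-off above 42 weeks would rise by about 17%.

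| Length (cm) | Printed (limit 0.88) | With limit 0.75 |
|---|---|---|
| 45 | 21.1 | 24.8 |
| 50 | 23.5 | 27.5 |
| 55 | 25.8 | 30.3 |
| 60 | 28.2 | 33.0 |

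**5. Exposure at the limit, relative to normal function.** AUC ratio = 1/[(1 − f) + f × GFR fraction], where f is the share of clearance that follows GFR. Both values of f are assumptions.

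| f | Two-thirds rule | 0.88, normal 0.50 | 0.88, normal 0.57 |
|---|---|---|---|
| 1.0 | 1.50 | 1.76 (17% higher) | 1.56 (4% higher) |
| 0.8 | 1.36 | 1.53 (12% higher) | 1.40 (3% higher) |

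**6. Reach.** Count each combination of gestational age (24+0 to 41+6, 126 days) and post-natal age (days 3–90, 88 days): 126 × 88 = 11,088. Those at or above 43+0 weeks number 3,486, or 31%. Among pre-term combinations it is 1,176 of 91 × 88 = 8,008, or 15%. Among term combinations it is 3,486 − 1,176 = 2,310 of 11,088 − 8,008 = 3,080, or 75%. These are age combinations, not expected patients.

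**The case against.** The strongest reply is that only one of two reasons for 0.88 fails. The other, a laboratory upper limit of normal for younger age groups, fits the number (1.32/1.5 = 0.88). The laboratory ranges are not in the documents, so a limit of 0.75 might exclude infants whose creatinine is normal for the local laboratory. This stands as a reason to check 0.75 before adopting it. It does not repair the row, because an upper limit for younger infants is not this age group's normal, and the row claims agreement with the 150% rule.

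The appendix also mixes two meanings of normal. The 28–34-week limit is 1.5 times an upper limit of normal, while the row above 42 weeks refers to a typical level. Against the mean of 0.68 mg/dL that the appendix cites for pre-term neonates (34 ± 3 weeks, days 3–7), 1.32 is 194%, or 52% of normal GFR. That is fair. It is why the point rests only on what the last row says about itself.

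Three stronger readings are tempting, and the documents do not support them:

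- **A reader might infer that 1.10 mg/dL at 35–42 weeks is wrong too, because it averages in 0.88.** Replacing 0.88 by 0.75 would give (1.32 + 0.75)/2 = 1.035. That averages a limit built on an upper limit of normal with one built on a typical level, and nothing in the documents shows 1.10 to be too high.
- **A reader might infer that the plan admits infants whom criterion 7 excludes.** The limits are advisory; criterion 7's own two-thirds wording, its other limbs and clinical judgement decide. Section 3.3.1 also says to stop ceftobiprole if eGFR falls below two-thirds of normal, and recommends real-time plasma levels if it is continued.
- **A reader might infer that the highest-dose infants are widely exposed.** Every infant in the 15 mg/kg q8h cell of Table 5 is above 42 weeks (the youngest is 37+0 plus 60 days, or 45+4). But that cell takes term infants only, Section 4.6 stops a group's enrolment at its minimum (two for term), and infants under 4 kg are capped at 10 mg/kg per dose.

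**Conclusion.** The row above 42 weeks is wrong as written. Its limit is 176% of the level it names, which the appendix's own rule converts to about 57% of normal GFR, or 64% if normal is 50 µmol/L. Either figure is below two-thirds, so the printed limit and its eGFR column are looser than criterion 7.

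The size is modest. At the limit, AUC would be 3% to 17% above what the two-thirds rule allows, depending on the reference level and on the assumed share of renal clearance. The limits are advisory, the band covers 15% of pre-term age combinations, and about two term infants are planned. How many enrolled infants would have creatinine between 0.75 and 0.88 mg/dL is not known. It is worth correcting because it is guidance for a renal safety criterion in a trial whose primary endpoint is safety, and the correction is cheap.

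**What to change.** In the row above 42 weeks, set the limit to 0.75 mg/dL and give the reason as 150% of 0.5 mg/dL, after checking 0.75 against the laboratory upper limit of normal for this age group. Recompute that eGFR column as 0.413 × length/0.75.

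If 0.88 is intended, keep it and correct the rationale. Either state the true ratio (176% of 0.5 mg/dL, about 57% of normal GFR) or name the reference level actually used (about 0.57 to 0.59 mg/dL), and say why the limit is consistent with criterion 7.

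Leave 1.32 and 1.10 as they are unless the sponsor re-derives the 35–42-week limit. If 0.75 is adopted, note that the 0.88 in the 35–42-week average is the laboratory upper limit, not the limit for the oldest group.

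Cost: one limit, one phrase and 28 table cells in an amendment, with no extra test. A few infants above 42 weeks with creatinine between 0.75 and 0.88 mg/dL would no longer pass the supporting limit, which could slow recruitment slightly.

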## LIST OF ABBREVIATIONS

|         |  |
|---------|--|
| ACM     | All-cause mortality                                |
| AE      | Adverse event                                      |
| AESI    | Adverse Event of Special Interest                  |
| ATC     | Anatomical Therapeutic Chemical                    |
| CE      | Clinically Evaluable                               |
| DSMB    | Data and Safety Monitoring Board                   |
| eCRF    | Electronic CRF                                     |
| EOT     | End-of-treatment                                   |
| ITT     | Intent-to-treat                                    |
| IV      | Intravenous  |
| LFU     | Last follow-up                                     |
| LOS     | Late-onset sepsis                                  |
| ME      | Microbiologically Evaluable                        |
| MedDRA  | Medical Dictionary for Regulatory Activities       |
| mITT    | Microbiological Intent-to-treat                    |
| PK      | Pharmacokinetic(s)                                 |
| PT      | Preferred Term                                     |
| SAE     | Serious adverse event                              |
| SAP     | Statistical Analysis Plan                          |
| SD      | Standard deviation                                 |
| SMQ     | Standardized MedDRA Queries                        |
| SOC     | System Organ Class                                 |
| TOC     | Test-of-cure                                       |
| WHO DDE | World Health Organization Drug Dictionary Enhanced |

## 1 INTRODUCTION

This document outlines the statistical methods to be implemented in the analysis of data collected within the scope of Basilea Pharmaceutica International Ltd., Allschwil, Protocol BPR-PIP-003 (A multicenter, open-label, single-arm, multiple-dose study to evaluate the safety, pharmacokinetics, and efficacy of ceftobiprole medocaril in term and pre-term neonates and infants up to 3 months of age with late-onset sepsis).

The purpose of this Statistical Analysis Plan (SAP) is to define the planned statistical methods in line with the study objectives. This plan should be read in conjunction with the study protocol (Version 5.0, dated 9 July 2024 at the time of finalization). All analyses will be conducted using SAS® Version 9.4 or higher.

## 2 OBJECTIVES

### 2.1 Primary objective

The primary objective of study BPR-PIP-003 is to characterize the safety profile of ceftobiprole medocaril in term and pre-term neonates and infants up to 3 months of age with late-onset sepsis (LOS).

### 2.2 Secondary objectives

The secondary objectives are to assess in term and pre-term neonates and infants up to 3 months of age with LOS treated with ceftobiprole medocaril:

- Pharmacokinetics (PK) of ceftobiprole
- Clinical response
- All-cause mortality (ACM)
- Microbiological response.

## 3 INVESTIGATIONAL PLAN

### 3.1 Overall study design

#### 3.1.1 Brief summary

This is a multicenter, open-label, single-arm, multiple-dose study of intravenous (IV) ceftobiprole in term and pre-term neonates and infants up to 3 months of age with LOS.

Study therapy consists of IV ceftobiprole medocaril for 3–10 days, which may be extended to 14 days if considered clinically necessary by the Investigator. Ceftobiprole may be combined with ampicillin and/or an aminoglycoside based on the Investigator's judgment, local standard of care, and/or isolated or presumed pathogens. If added, the treatment duration of ampicillin and/or an aminoglycoside is at the discretion of the Investigator.

Each patient is expected to complete the study in approximately 5–7 weeks, including screening, an estimated treatment duration of 3–10 days with possible extension up to 14 days, end-of-treatment (EOT) visit, test-of-cure (TOC) visit 7–14 days after last ceftobiprole dose, and a last follow-up (LFU) visit 28–35 days after last ceftobiprole dose.

Safety assessments will be done throughout the study. Specimens for microbiological assessment will be obtained as clinically indicated in accordance with local standard of care. Blood samples for PK analysis will be collected on Day 3. Efficacy outcomes will be assessed at the EOT, TOC, and LFU visits.

An overview of the study design is provided in protocol Section 3. The schedule of assessments and procedures for the different periods are provided in protocol Section 5.1.

An independent Data and Safety Monitoring Board (DSMB) will review patient data on an ongoing basis to determine whether any safety concerns are observed, and whether the study should be allowed to continue, as specified in the DSMB Charter.

### 3.1.2 Number of patients

At least eight patients will be enrolled in the study, comprising at least two term patients (gestational age  $\geq$  37 weeks) and at least six pre-term patients (gestational age  $\geq$  24 to 36 weeks), with post-natal age ranging from  $\geq$  3 days to  $\leq$  3 months.

### 3.1.3 Treatments

Eligible patients will receive ceftobiprole as a 2-hour IV infusion according to the schedule in [Table 1](#), with dose adjusted according to gestational and post-natal ages. Body weight on Day 1 should be obtained within 12 hours prior to the first dose of study drug. From Day 2 until the last day of study treatment, the dose should be calculated based on the patient's first body weight of the day.

**Table 1 Ceftobiprole dosing regimen for the treatment of neonates and infants with late-onset sepsis**

| Gestational age group (weeks) | Post-natal age (days) |                |                |                |
|-------------------------------|-----------------------|----------------|----------------|----------------|
|                               | 3 – 13                | 14 – 29        | 30 – 59        | 60 – 90        |
| 24 – 26                       | 7.5 mg/kg q12h        | 7.5 mg/kg q12h | 10 mg/kg q12h  | 10 mg/kg q12h  |
| 27 – 31                       | 10 mg/kg q12h         | 10 mg/kg q12h  | 10 mg/kg q12h  | 15 mg/kg q12h* |
| 32 – 36                       | 10 mg/kg q12h         | 10 mg/kg q12h  | 15 mg/kg q12h* | 15 mg/kg q12h* |
| $\geq$ 37                     | 15 mg/kg q12h*        | 15 mg/kg q12h* | 15 mg/kg q12h* | 15 mg/kg q8h*  |

Note: All doses will be infused over 2 hours. The maximum allowable dose in adult and pediatric patients is 500 mg regardless of body weight.

\* Neonates and infants with a body weight  $<$  4 kg should receive a maximum of 10 mg/kg/dose.

## 3.2 Study endpoints

### 3.2.1 Primary endpoints

The primary endpoint is safety and tolerability in the Safety population, as assessed by adverse events (AEs), serious adverse events (SAEs), deaths, and discontinuations due to AEs during treatment with ceftobiprole and at the EOT, TOC, and LFU visits, as well as clinical laboratory tests, vital signs, and physical examination findings.

### 3.2.2 Secondary endpoints

The pharmacokinetics secondary endpoints are:

- Plasma levels of ceftobiprole, ceftobiprole medocaril, and open-ring metabolite (PK population).

The efficacy secondary endpoints are:

- Clinical cure rate at the EOT and TOC visits [Intent-to-treat (ITT) and Clinically Evaluable (CE) populations]
- ACM through Day 28 (ITT population)
- Microbiological eradication or presumed eradication rate at the EOT and TOC visits (Microbiological Intent-to-treat (mITT) and Microbiologically Evaluable (ME) populations)
- Improved signs and symptoms of LOS at the Day 3, EOT, and TOC visits (ITT and CE populations).

